3.0 Patient Eligibility Criteria and Registration

3.1 Patient Registration

This is a multi-institution study between UCSD/Rady Children's Hospital and Emory University/Children's Healthcare of Atlanta. UCSD/Rady Children's Hospital will be the coordinating site for this investigator initiated trial.

Eligible patients will be registered by contacting the Clinical Research Coordinator, Monday through Friday, 8:00 am-5:00 pm Pacific Standard Time by phone except on holidays. Calls will be returned within one business day. The research coordinator will review preliminary eligibility by phone before forwarding a registration packet to the

enrolling practitioner. The information requested in the registration packet must be completed. The signed informed consent statement along with the documentation confirming eligibility must be faxed. Upon receipt of the completed registration packet, the research coordinator will assign a unique patient registration number and study subject number. **Patients must be registered prior to starting any protocol therapy.**

Contact Person: [name], BSN, CCRC
Oncology Research Center
UCSD/Rady Children's Hospital
[name]
San Diego, CA 92123
[contact]
[contact]

Important note: The eligibility criteria listed below are interpreted literally and cannot be waived. Patients must begin treatment within two weeks of study registration. Registration will be completed only after pathologic diagnosis is confirmed by central review (please see below).

Between the two sites, we anticipate enrolling up to 10-15 subjects per year, to achieve a total of 24 evaluable subjects. Thus we are confident that accrual can be completed within 2-3 years. The estimation is reflected by the number of patients with recurrent low grade glioma tumors that are treated annually at Rady Children's Hospital and Children's Healthcare of Atlanta.

3.2 Inclusion Criteria

3.2.1 Age

Subjects must be between 0 – 21 years of age when enrolled on this protocol.

3.2.2 Diagnosis

Subjects must have pathologically confirmed low grade glioma with histologic subtypes interpreted as WHO grade I and II including:

- juvenile pilocytic astrocytoma (JPA)
- pleomorphic JPA
- diffuse astrocytoma (fibrillary, gemistocytic, giant cell, or pleomorphic xanthoastrocytoma)
- subependymal giant cell astrocytoma (SEGA)
- low grade oligoastrocytoma
- low grade oligodendrogloma
- pilomyxoid astrocytoma
- low grade glioma NOS

Tumors of all regions of the CNS, with appropriate histology are eligible for study. However patients with SEGA or tumors intrinsic to the optic nerve and involvement of the optic nerve that cannot be biopsied/resected are eligible without histological confirmation.

Subjects with neurofibromatosis type 1(NF1) are also eligible (see appendix II for NF1 diagnostic criteria).

All pathologic diagnoses of subjects from all enrolling sites will be confirmed with tissue block review of previously obtained specimens by [name]., Ph.D. This will be done in order to assure

uniformity in the above subtypes for these sometimes difficult to diagnose tumors. Once consent is obtained, subjects' tissue/slides and corresponding pathology report should be forwarded for central review at UCSD. These samples should be sent to:

[name]., Ph.D.
Professor of Pathology
Director of Neuropathology
University of California, San Diego
Pathology, MC 0612
BSB Room 2008
[name]
La Jolla, CA 92093-0612
[contact]

3.2.3 Criteria

Subjects must have demonstrated either tumor progression or recurrence by any of the radiographic criteria and/or clinical criteria as defined below:

- a. Subjects with progressive non-resectable disease regardless of location in the brain or spine are eligible for this study. Patients with evidence of leptomeningeal dissemination are eligible for this study. Patients do not require biopsy/histologic confirmation at the time of progression or relapse.
- b. Radiographic progression is defined as >40% increase in the product of the three perpendicular diameters of current tumor relative to the baseline measurement (defined as either the initial scan or scan at start of a previous therapy):
length (L) x width (W) x transverse (T) (current scan) $> 1.4 \times L \times W \times T$ (baseline scan), or the development of any new sites of disease independent of the response of the initial tumor.
See section 7.1.2 for methodology for tumor measurement.
- c. Post radiation changes are often seen on post-treatment imaging studies, so that classification of a patient as having progressive disease may require several serial MRI's if the child has received radiation within the preceding 12 months.
- d. Tumor volume includes the entire tumor volume seen on gadolinium enhanced T1 MR imaging plus non-enhancing abnormality seen on T2 or FLAIR. Coronal and axial images will be evaluated.
- e. All tumor cysts will be included in the tumor volume
- f. Clinical progression without radiographic progression includes children with optic pathway gliomas who demonstrate sustained decrease in visual fields and/or acuity in three serial vision examinations. Each of the vision examinations must be performed >2 weeks apart.
- g. Children with previously negative cerebrospinal fluid (CSF) cytology who show evidence of tumor cells in fluid obtained by lumbar puncture can be designated as having progressive disease in the absence of radiographic evidence of progression.

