3.2.5 Prior Therapy

Subjects must have fully recovered from the acute toxic effects of all prior chemotherapy, immunotherapy, or radiotherapy prior to entering this study and meet time restrictions from end of prior therapy as stated below:

- a. Myelosuppressive chemotherapy: Subjects must have received the last dose of myelosuppressive therapy at least 3 weeks prior to study registration or at least 6 weeks if therapy included nitrosourea.
- b. Investigational / Biological agent: Subjects must have received the last dose of other investigational or biological agent >7 days prior to study registration. Subjects must not have received polyICLC in the past.
- c. XRT: Subjects must be ≥ 8 weeks since the completion of radiation therapy.
- d. Study specific limitations on prior therapy: There is no limit on the number of prior treatment regimens or received doses of radiation therapy.
- e. Growth factor(s): Subjects must not have received any hematopoietic growth factors within 7 days of study entry or 21 days for pegfilgastrim.
- f. Prior Surgery: Subjects must be ≥ 2 weeks from prior surgery.
- g. Steroids: Subjects must be on a stable steroid dose for 7 days prior to study entry if they are on steroid treatment.

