Subjects who travel to the coordinating or enrolling sites for protocol therapy may return home to the care of their primary pediatric oncologist after completing cycle 1 of therapy for standard of care management at the discretion of the study physician/committee. Subjects will be seen and monitored by their primary treating oncologist at the start of each cycle. For those subjects, a 3 month supply of study drug will be dispensed to the subject/family from their enrolling site. The enrolling site will continue to see the subject every 3 months for evaluation and will remain responsible for continued data capture of all required information.

4.2: Dose modifications based on Toxicity

If AST/ALT > 10x ULN while on study, Poly ICLC will be discontinued until the AST/ALT are < 5x ULN; the study drug will then be restarted at 20 mcg/kg/dose twice weekly (the initial dose).

If AST/ALT > 10x ULN for a second time, hold study drug until values < 2.5x ULN; then restart drug at the reduced dose of 10 mcg/kg/dose twice weekly.

Study drug will be stopped and subject will be off treatment for toxicity if AST/ALT do not decrease to < 5x ULN during the first episode and <2.5x ULN at second episode when drug is held for three weeks.

For the NF 1 cohort, consider restarting drug again at 5 mcg/kg/dose twice weekly if toxicities recur at the prior reduced dose of 10mcg/kg/dose.

For all other grade 3 or grade 4 toxicities the same dose modifications will be followed. The study drug will be held until resolution of these toxicities to ≤ grade 1. If the toxicity is not resolved within 3 weeks of the last dose of the study drug administration the subject will be taken off protocol therapy.

4.3: Concomitant Therapy

Corticosteroids and anticonvulsants may be given as indicated clinically. However, if the dose of steroids is increased while on therapy, MRI must be performed to rule out disease progression. Acetaminophen may be given as needed to control poly-ICLC side effects. A non-P450 inducing anticonvulsant will be used while on this study (see Appendix 3).

Radiotherapy may not be given while on study to the lesions being utilized as measurable disease in order to assess response. Patients may enter on study after completion of involved field radiation therapy, however at least 8 weeks should elapse after radiation, and scans should show residual disease prior to entry on study. Chemotherapy is not allowed.

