7.0 RESPONSE CRITERIA

MRI Response Criteria: Comparison of objective assessments are based on major changes in tumor size compared to the baseline scan. Determination of progressive disease is based on tumor measurements described below.

Interpretation of anatomic (MRI) response rates in gliomas can be difficult. Tumors may be non-enhancing, and certain area of enhancement may represent post-operative or radiation change. Shrinkage of enhancing lesions can also be seen for months after radiation alone. These factors may confound the MRI interpretation of tumor response to poly-ICLC. Also in the Principal investigator's previous experience, tumor regression or stabilization on MRI was seen at 12 and 52 months in some patients on poly ICLC. Hence in the absence of clearly progressive disease (worsening neurological status, significant increase in tumor size on MRI), poly-ICLC should be continued for possible late benefits.

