7.1.3 Tumor Response Criteria Based on 3 Dimensional Measurements

- a. Complete Response (CR): Disappearance of all measurable and evaluable tumors. There are no new lesions and no evidence of non-evaluable disease.
- b. Partial Response (PR): $> 65\%$ decrease in the sum of the products of the three perpendicular diameters of the measurable tumors relative to the sum of products of initial baseline measurements - $LxWxT$ (current scan) $< 0.65 * LxWxT$ (initial scan). There is no progression of evaluable disease and no new lesions.
- c. Stable disease (SD): Neither sufficient decrease in the product of the three perpendicular diameters to qualify for partial response nor sufficient increase to qualify for progressive disease.
- d. Progressive Disease (PD): $>25\%$ increase in the sum of products of the three perpendicular diameters of the measurable tumors relative to the initial baseline measurement - $LxWxT$ (current scan) $> 1.25 * LxWxT$ (initial

scan) **or** the development of any new sites of disease. As post-radiation changes are often seen on post-treatment imaging studies, classification of a patient as having progressive disease may require several serial MRIs.

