- Association of baseline levels of proteins (such as OAS, interferon, PKR, phosphorylation state of eIF2a, p21^{waf-1}) in serum, PBMC and/or cerebrospinal fluid with progression free survival.
- Association of changes in levels of proteins (such as OAS, interferon, PKR, phosphorylation state of eIF2a, p21^{waf-1}) serum, PBMC and/or cerebrospinal fluid from baseline with tumor response status at 6 months after treatment with Poly-ICLC.
- Association of changes in levels of proteins (such as OAS, interferon, PKR, phosphorylation state of eIF2a, p21^{waf-1}) in serum, PBMC and/or cerebrospinal fluid from baseline with progression free survival.

9.1: Study Design and Justification of Sample size

9.1.1 This is a single arm study, to determine the radiographic progression free survival (PFS) rate to poly-ICLC in the treatment of children with recurrent or progressive low grade gliomas. The primary endpoint is the progression free survival status at 6 months (PFS6) after starting therapy. The tumor response categories will include complete response, partial response, stable disease or progressive disease, as assessed according to section 7.1.2.

Simon's optimal two-stage design will be used for this study (Simon, 1989). Suppose 50% is the uninteresting level, i.e., if the PFS6 rate is $\leq 50\%$, we will consider the new regimen as not promising. This 50% baseline response rate in the absence of treatment is from historical experience (this rate was also used by the Everolimus study which is a phase II study for recurrent or progressive LLG in children), also taking into account that this study patient population are more refractory. We will test the null hypothesis $H_0: p \leq 50\%$ against the alternative hypothesis $H_1: p > 75\%$, where p is the PFS6 rate. The two stage design proposed below will have 80% power to reject the null and conclude that the true response rate is above 50%, if the true response rate is $\geq 75\%$, at 5% significance level.

The study design can be described in detail as follows:

Stage 1: Fourteen subjects will be accrued; accrual will be held up until the PFS6 results for all the 14 subjects are known. The trial will be terminated at Stage 1 if ≤ 7 subjects have a PFS6 response; otherwise it continues to Stage 2. Note that any subject who goes off study early due to toxicity, will be counted as a non-response (an intent to treat analysis).

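### Does entry from 8 weeks after radiation, without proof of growth since, call for a planned PFS6 breakdown by prior radiation?

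*Combined protocol and SAP*

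**What the plan says.** **Entry.** Section 3.2.3 b requires the product of three diameters to exceed 1.4 times its earlier value, taken "relative to the baseline measurement (defined as either the initial scan or scan at start of a previous therapy"), or a new site. Items f and g add entry by visual loss or by CSF cytology. Section 3.2.3 c notes that several scans may be needed to classify progression "if the child has received radiation within the preceding 12 months".

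**Prior radiation.** Section 3.2.5 c sets a minimum of 8 weeks since radiation. Item d adds: "There is no limit on the number of prior treatment regimens or received doses of radiation therapy". Section 4.3 says of irradiated patients: "however at least 8 weeks should elapse after radiation, and scans should show residual disease prior to entry on study".

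**Reading the scans.** Section 7.0 warns: "Shrinkage of enhancing lesions can also be seen for months after radiation alone". It then says: "These factors may confound the MRI interpretation of tumor response to poly-ICLC". For the secondary three-dimensional criteria, section 7.1.3 d allows for this: "As post-radiation changes are often seen on post-treatment imaging studies, classification of a patient as having progressive disease may require several serial MRIs". Section 7.1.2, which governs the primary endpoint, has no such sentence.

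**Test.** Section 9.1.1 takes a null PFS6 of 50% and explains: "This 50% baseline response rate in the absence of treatment is from historical experience", with an allowance for a more refractory population. The design stops at 7 or fewer of 14, and section 9.1.4 declares success at 16 or more of 23. Section 9 splits feasibility and toxicity by NF1 status and relates markers to response. It plans no split of PFS6 by prior radiation or by timing of growth.

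**The concern.** Suppose a tumour grew past 1.4 times its first-scan size, was irradiated, and 8 weeks later is still above 1.4 times that size. Read literally, the child qualifies without any growth since radiation. Six months of stable disease then counts as a PFS6 success, although section 7.0 says that radiation alone can keep shrinking a lesion for months. With no control arm, nothing inside the trial separates that success from a drug effect.

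The opposite error is also possible. Post-radiation enlargement could be scored as progression under section 7.1.2, which lacks the serial-scan allowance, and an active drug would be penalised.

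The stake is the meaning of a pass or a fail at 16 of 23. If many such children enrolled, the fixed 50% would be the wrong yardstick, and the plan commits to no summary that would show it.

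**Working it through.** **1. Reproduce the design.** Inputs from section 9.1: 14 subjects in stage 1, continue at 8 or more; 9 more in stage 2; success at 16 or more of 23; p0 = 0.50, p1 = 0.75.

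P(success) = sum over x1 = 8 to 14 of P(X1 = x1) × P(X2 ≥ 16 − x1), with X1 ~ Bin(14, p) and X2 ~ Bin(9, p).

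- p = 0.50: 0.0462 (stated limit 5%)
- p = 0.75: 0.8016 (stated power 80%)
- P(X1 ≤ 7) at p = 0.50: 0.6047 (stated 61%)

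The stated figures reproduce, within a point for early stopping.

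**2. Who is affected.** A tumour that radiation has brought below 1.4 times the reference fails the size test. A child whose tumour regrew after radiation is properly progressive. What remains is the irradiated child who still meets an entry criterion and has not regrown. The documents do not give this number. Section 2.0 describes chemotherapy as a way to avoid or delay radiation in young patients and argues for avoiding it up to age 10, which suggests a limited irradiated share, although ages 0 to 21 are eligible.

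**3. Size, with the unknowns as assumptions.** Let k of the 23 be such children with PFS6 rate q, and the rest have rate p. Then X1 is Bin(k1, q) + Bin(14 − k1, p), and X2 is Bin(k2, q) + Bin(9 − k2, p). I split k = 1, 2 and 5 across the stages as 1+0, 1+1 and 3+2. The false-success columns use p = 0.50 (no drug effect). The power column uses p = 0.75 and q = 0.55, that is, 20 points lost to enlargement read as progression.

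| k | False success, q = 0.30 | q = 0.70 | q = 0.80 | Power, q = 0.55 |
|---|---|---|---|---|
| 0 | 4.6% | 4.6% | 4.6% | 80.2% |
| 1 | 3.8% | 5.4% | 5.8% | 77.3% |
| 2 | 3.1% | 6.3% | 7.3% | 74.4% |
| 5 | 1.6% | 9.9% | 13.7% | 64.4% |

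One or two such children move the error rates by a few points, in a direction the documents do not settle. Five would matter, but nothing in the documents points to five.

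**4. What a pre-specified summary would show.** Take a bare pass, 16/23 (exact one-sided lower 90% limit 54.1%, ignoring the two-stage design), and exclude 3 recently irradiated subjects. If radiation had no bearing on outcome, the number of successes among those 3 is hypergeometric:

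| Successes removed | Remaining | Lower 90% limit | Chance |
|---|---|---|---|
| 0 | 16/20 | 63.9% | 2.0% |
| 1 | 15/20 | 58.5% | 19.0% |
| 2 | 14/20 | 53.3% | 47.4% |
| 3 | 13/20 | 48.2% | 31.6% |

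Chance alone spreads the result from 13/20 to 16/20, with limits on both sides of 50%. In the excluded group itself, 2 of 3 has an exact 95% interval of 9% to 99%. The exclusion would also remove children with true regrowth after radiation, who are not the concern.

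**The case for a change.** The strongest case for a change is that section 7.0 names the confounder and section 9 then does nothing with it. A single-arm result is sensitive to case mix: with no drug effect, false success is 4.6% at a true PFS6 of 50% but 11.4% at 55%. Section 3.2.3 c is discretionary and is aimed at false growth, not at real growth that came before radiation. The allowance for a more refractory population is unquantified and does not mention radiation. A summary fixed in advance carries more weight than one chosen after the data are seen, and the end date of radiation is needed anyway to check section 3.2.5 c.

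Most of this stands as fact. It does not show that a rule or number in the plan gives a wrong result. Moving the whole population from 50% to 55% illustrates any single-arm test; it is not an estimate of a radiation effect. The requested tables would carry no threshold, so advance specification protects little. The added item is also less simple than it sounds: telling whether growth followed the last therapy needs a scan between that therapy and entry, which the protocol does not require, so some subjects would be unknown. On false progression, the pre-study MRI falls within 14 days of entry and at least 8 weeks after radiation, so enlargement already present then is part of the baseline. Later enlargement is not covered, and section 7.1.2 does lack the allowance.

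**Conclusion.** No change to the plan. Literal entry without growth since radiation is possible, and section 9 has no PFS6 breakdown that would reveal it. The affected group is narrow, though, and its number and drug-free PFS6 cannot be found from the documents. If it is one or two of 23 with a drug-free PFS6 of 30% to 70%, and the rest are at 50%, false success lies between 3.1% and 6.3% against 4.6%. If the drug gives 75% and these children lose 20 points to misread enlargement, power is 77.3% or 74.4% against 80.2%. A larger group would weaken this conclusion.

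Section 9.0 sets out to obtain preliminary estimates, and an extra summary of a handful of children would alter neither the decision rule nor the conclusion. A sensible analyst will list PFS6 beside radiation history, and beside the timing of growth where scans allow, as description only. That is a reporting choice and needs no amendment.

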3.2.4 Performance Level and Life Expectancy

Subjects must have a performance status of > 50% (Appendix I). Use Karnofsky for patients > 16 years of age and Lansky for patients ≤ 16 years of age. Subjects must have a life expectancy of ≥ 8 weeks.

3.2.5 Prior Therapy

Subjects must have fully recovered from the acute toxic effects of all prior chemotherapy, immunotherapy, or radiotherapy prior to entering this study and meet time restrictions from end of prior therapy as stated below:

- a. Myelosuppressive chemotherapy: Subjects must have received the last dose of myelosuppressive therapy at least 3 weeks prior to study registration or at least 6 weeks if therapy included nitrosourea.
- b. Investigational / Biological agent: Subjects must have received the last dose of other investigational or biological agent >7 days prior to study registration. Subjects must not have received polyICLC in the past.
- c. XRT: Subjects must be ≥ 8 weeks since the completion of radiation therapy.
- d. Study specific limitations on prior therapy: There is no limit on the number of prior treatment regimens or received doses of radiation therapy.
- e. Growth factor(s): Subjects must not have received any hematopoietic growth factors within 7 days of study entry or 21 days for pegfilgastrim.
- f. Prior Surgery: Subjects must be ≥ 2 weeks from prior surgery.
- g. Steroids: Subjects must be on a stable steroid dose for 7 days prior to study entry if they are on steroid treatment.

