5.0 Required Observations

All Pre-study Observations must be done within 14 days of study entry.

Observation	Pre-Study	Day 1 of Cycle 1	Day 15 of Cycle 1	Prior to subsequent cycles 2-12	Prior to subsequent cycles 13-24	End of therapy/Off Study
History, VS, Physical	x	x	x	x	x	x
Performance Status ¹	x	x	x	x	x	x
Toxicity Evaluation			x	x	x	x
Neuro Evaluation	x	x	x	x	x	x
Concomitant Meds	x	x	x	x	x	x
CBCD, Platelets	x	x	x	x	x	x
PT/PTT	x	x	x	x†	x†	x†
CMP w/Phos	x	x	x	x	x	x
Urinalysis ³	x					
Serum Pregnancy ³	x					
MRI-Brain/Spine**	x			Every 3 cycles starting with end of Cycle 3↑	End of Cycle 18 and 24 only†	x
LP/CSF cytology*	x			Every 3 cycles starting with end of Cycle 3 ²	End of Cycle 18 and 24 only ²	x ²
Biology-red & purple top blood samples		x	x			
Data Collection Submission ⁴	x			x	x	x

1:Performance Status=Karnofsky if > 16 y/o or Lansky if ≤ 16 y/o

2: repeat only if cytopathology showed tumor cells at study entry or disease progression

3: Repeat as needed for good clinical care

4: Data Collection should be submitted monthly

†: Repeat PT/PTT only if abnormal after Day 15

↑ Repeat MRI Spine only if not normal pre study

* Lumbar Puncture/CSF cytology is not required if already done within 4 weeks of study entry.

CSF will be obtained prior to initiation of therapy with Poly ICLC. If positive, CSF will be obtained at 3, 6, 9, 12, 18, 24 months after study entry, as well as the time end of therapy/off study.

MRI Brain/Spine should be obtained with and without gadolinium including pre T1, post T1, T2 and flair sequences. Both axial and either coronal or sagittal pre-post gadolinium images should be obtained.

MRI will be assessed at 3, 6, 9, 12, 18, 24 months after starting the therapy (at the end of those cycles), as well as at the time end of therapy/off study or if subject is going off study prematurely.

**MRI spine does not have to be repeated during the study if it was normal pre-study. It should be repeated at the time end of therapy/off study or if subject is going off study prematurely.

A copy of the MRI images on a CD should be sent to the coordinating site.

5.1: Pretreatment Evaluation (must be performed within 14 days of study entry)

- A. History, vital signs and physical examination, including neurologic evaluation and concomitant medication list
- B. CBC, differential, platelet count, PT/PTT
- C. AST, ALT, alkaline phosphatase, albumin, calcium, phosphorus, total bilirubin
- D. BUN, Cr, urinalysis

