- E. Disease evaluation with either MRI of brain/spine and CSF cytology. (LP is not required if already done within 4 weeks of study entry).
- F. Serum B-HCG in females of childbearing age
- G. Lansky Play Scale assessment for patients ≤ 16 years of age; Karnofsky score for patients >16 years old. (see Appendix I).
- H. Study entry form/eligibility check list to be filled out prior to starting treatment.

5.2: Evaluation during treatment

- A. Disease evaluation (including MRI), if positive at study entry, every 3 cycles for the first 12 cycles (to be done at the end of the cycle), then every 6 cycles for as long as the subject remains on study. MRI spine does not have to be repeated if it was normal pre-study. Disease status and events form is to be filled every 3 months for the first 12 months and then every 6 months while subject is on study.
- B. History, vital signs, physical examination and concomitant medication list at day 1 and day 15 of cycle 1, and then prior to each cycle (monthly for as long as the patient remains on study).
- C. Labs are to be obtained at day 1 and day 15 of cycle 1, and then prior to each cycle (monthly for as long as the subject remains on study).
 - CBC/differential, platelets
 - Chemistry panel including: AST, ALT, alkaline phosphatase, albumin, calcium, phosphorus, total bilirubin, BUN, Cr
 - PT/PTT at Cycle 1 Day 1 and 15, repeat further only if abnormal
- D. Neurologic assessment at each visit with scoring of overall exam compared to previous exam as follows: No change from previous exam; worsening from previous exam; improvement from previous exam.
- E. Record at each visit if steroids are being given and if dose is same, lower, higher than at previous visit. MRI required if steroid dose increased.
- F. Toxicity monitoring form and Lansky Play Scale assessment for subjects ≤ 16 years of age; Karnofsky score for subjects >16 years old. (see Appendix I) at week 2 and then prior to each cycle.

5.3: Evaluation at the end of therapy or relapsed disease

- A. Disease evaluation (including MRI brain and spine) and lumbar puncture for CSF cytology (required only at time of disease progression) with all studies that were initially positive at study entry
- B. History, vital signs, physical examination, and concomitant medication list
- C. Labs:
 - CBC/differential, platelets
 - Chemistry panel including AST, ALT, alkaline phosphatase, albumin, calcium, phosphorus, total bilirubin, BUN, Cr
 - PT/PTT, if still abnormal

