7.1.2 Tumor Response Criteria on 2 Dimensional Measurements (per Modified MacDonald Criteria)

- a. Complete Response (CR): Complete disappearance of all measurable and evaluable disease. There are no new lesions and no evidence of non-evaluable disease. All measurable, evaluable and non-evaluable lesions and sites must be assessed using the same techniques as baseline. Patients must not be on any steroids.
- b. Partial Response (PR): $\geq 50\%$ decrease over baseline in the sum of products of perpendicular diameters of all measurable lesions. There is no progression of evaluable disease and no new lesions. All measurable and evaluable lesions and sites must be assessed using the same techniques as baseline. The steroid dose at the time of the scan should be no greater than the maximum dose during the first 8 weeks since initiation of therapy.
- c. Stable Disease (SD): Does not qualify for CR, PR, or progression. All measurable and evaluable sites must be assessed using the same techniques as baseline. The steroid dose at the time of the scan should be no greater than the maximum dose used during the first 8 weeks since initiation of therapy.
- d. Progressive Disease (PD): $\geq 25\%$ increase in the sum of products of all measurable lesions over baseline using the same techniques as baseline, **or** clear worsening of any evaluable disease, **or** appearance of any new lesion/site, **or** clear clinical worsening **or** failure to return for evaluation due to death or deteriorating condition (unless clearly unrelated to this cancer).

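### The baseline MRI may be taken up to 14 days before study entry but a stable steroid dose is required only for the last 7, so the size reference for progression can be on a different steroid dose in some children

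*Combined protocol and SAP*

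**What the plan says.** Three timing rules bear on the baseline scan.

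- Section 3.2.5(g), steroids: "Subjects must be on a stable steroid dose for 7 days prior to study entry if they are on steroid treatment".
- Section 5.0: "All Pre-study Observations must be done within 14 days of study entry". The MRI belongs to these observations. Section 5.1, item E, lists it ("Disease evaluation with either MRI of brain/spine and CSF cytology") under the same 14-day limit, and only the lumbar puncture has a separate allowance of 4 weeks.
- Section 3.1: "Patients must begin treatment within two weeks of study registration".

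The scan is then the reference for response. Section 7.0 says "Comparison of objective assessments are based on major changes in tumor size compared to the baseline scan", and the size criterion for progression in 7.1.2(d) is a 25% or greater "increase in the sum of products of all measurable lesions over baseline using the same techniques as baseline".

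Steroids enter the response criteria in two places. In 7.1.2, complete response requires that the child be off steroids. Partial response and stable disease require a dose at the scan "no greater than the maximum dose during the first 8 weeks since initiation of therapy" (the wording for partial response; the stable-disease clause is equivalent). The progression definition has no steroid condition. Section 4.3 adds that "if the dose of steroids is increased while on therapy, MRI must be performed to rule out disease progression".

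**The concern.** The stability rule counts back from study entry and is not tied to the date of the scan. A child can be scanned in the first half of the 14-day window, have the steroid dose changed, complete 7 stable days and enter the study with every rule met. Later scans are then compared with a tumour measured under a different steroid dose.

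The protocol itself treats steroid dose as relevant to reading the scans: it restricts dose in the response categories and requires an MRI after an increase on therapy. The primary endpoint, PFS6, depends on progression measured against this one scan. An inflated baseline makes size progression harder to reach and a reduced one makes it easier, and the same baseline serves every later size comparison in that child.

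**Working it through.** **1. The plan's own figures.** The documents derive no number from these windows. The design figures that depend on the endpoint are those of the two-stage rule in 9.1: stop if 7 or fewer of 14 succeed, and declare success at 16 or more of 23.

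P(success declared) = Σ over x = 8 to 14 of Bin(x; 14, p) × P(X₂ ≥ 16 − x | 9, p)

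- p = 0.50: 0.0462 (stated level 5%).
- p = 0.75: 0.8016 (stated power 80%).
- Early stopping at p = 0.50: 0.6047 (stated 61%).

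The design reproduces closely, and nothing below changes it.

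**2. The windows.**

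| Interval | Length | Stable dose required? |
|---|---|---|
| Days −14 to −8 before entry | 14 − 7 = 7 days | No |
| Days −7 to entry | 7 days | Yes |
| Entry to first dose, if entry is registration | up to 14 days | No |
| Entry to first dose, if entry is treatment start | 0 days | Not applicable |

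Scan to first dose can reach 14 + 14 = 28 days on the first reading of entry and 14 days on the second. Section 3.2.5 speaks of registration in items (a) and (b) and of study entry in (e) and (g), without defining the latter. Only the 7-day gap holds on both readings.

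**3. Whether another rule closes the gap.**

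- The 8-week clause for partial response and stable disease looks forward from the start of therapy. Steroids begun after the scan and still given in those 8 weeks count towards the permitted maximum, so the mismatch passes.
- The progression definition has no steroid condition.
- The MRI required in 4.3 after a dose increase applies only on therapy.
- Concomitant medication is listed pre-study and on Day 1 of Cycle 1 (5.0, 5.1 A, 5.2 B), and each visit records whether the steroid dose is the same, lower or higher than at the previous visit (5.2 E). No rule uses these records to repeat, qualify or flag the baseline scan.

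**4. Effect on the progression threshold.** Let s be the fraction by which steroids reduce measured area. The documents give no value, so s = 0.10, 0.20 and 0.30 are assumed.

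- Steroids start after the scan: later areas are multiplied by (1 − s), so the threshold is met at true growth of 1.25/(1 − s) − 1.
- Steroids are tapered after the scan: the baseline was multiplied by (1 − s), so the threshold is met at true growth of 1.25 × (1 − s) − 1.

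| s | Started after scan | Tapered after scan |
|---|---|---|
| 0.10 | 1.25/0.90 − 1 = 39% | 1.25 × 0.90 − 1 = 12.5% |
| 0.20 | 1.25/0.80 − 1 = 56% | 1.25 × 0.80 − 1 = 0% |
| 0.30 | 1.25/0.70 − 1 = 79% | 1.25 × 0.70 − 1 = −12.5% |

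With matched doses the figure is 25%.

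**5. Partial response.** For an unchanged tumour with steroids started after the scan, the apparent decrease is s, that is 10, 20 or 30%. Partial response needs at least 50%, so these effects alone do not produce one.

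**6. Sensitivity of the decision rule, for scale only.** Let m be an assumed share of children misclassified at 6 months.

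- True successes called progression: p = 0.75 × (1 − m). For m = 2, 5 and 10%, power is 75, 67 and 51%.
- True failures called progression-free: p = 0.50 + 0.50 × m. For the same m, type I error is 5.6, 7.4 and 11.4%.

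No value of m can be taken from the documents.

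**The case against.** The two windows do not contradict each other, and the reach is narrow. Only children whose steroid dose changed between the baseline scan and the first dose are affected, and the documents do not say how many there are. Progression can also be called on a new lesion, clear worsening of evaluable disease or clear clinical worsening, none of which uses the baseline product. The pre-study and Day 1 medication records should make a change visible. All of this stands and limits the point. It does not remove it, because the size criterion remains exposed and no analysis rule draws on those records.

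Three stronger readings are tempting.

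- A reader might infer that steroid-related shrinkage would be scored as response. Step 5 shows that assumed effects of 10 to 30% fall short of a partial response on their own. Partial response and stable disease are in any case both progression-free, so for PFS6 only the progression boundary matters.
- A reader might infer from step 6 that the trial loses power or exceeds its 5% level by those amounts. The misclassification rates are invented for scale, and nothing in the documents links them to steroid changes.
- A reader might take 28 days from scan to first dose as established. That holds only if study entry means registration.

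Section 7 also does not define the baseline scan. The pre-study MRI is the only scheduled scan before treatment, so reading it as the baseline is natural but is still an interpretation.

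**Conclusion.** The gap is real and limited. The text allows the baseline MRI to fall in 7 days not covered by the steroid-stability rule, plus up to 14 more before first dose if entry is registration. For a child whose dose changes after the scan, the 25% size threshold can correspond to true growth well above or well below 25%, so PFS6 can err in either direction.

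The per-child figures rest on assumed steroid effects of 10 to 30% and apply only to progression by size. The effect on the trial's PFS6 rate cannot be estimated, because the number of affected children is not given. This is a cheap improvement to baseline measurement. It does not show that the primary analysis is biased, and the sample size, level and power of the design are unaffected.

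**What to change.** Reconcile sections 3.1, 3.2.5(g), 5.0/5.1 and 7.1.2 as follows.

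1. Define study entry relative to registration and first dose.
2. Schedule the baseline MRI within the protocol's own stable-steroid period, and state in section 7 that this scan is the baseline.
3. Record the actual steroid dose at the baseline MRI and at each later MRI. The present visit record gives only the direction of change, and the pre-study medication list is not tied to the scan date.
4. Add a sensitivity analysis of PFS6 that flags children whose dose differed between the baseline MRI and Day 1 of Cycle 1. This also covers any change between entry and first dose.

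This concerns when the scan is taken and what is recorded. It sets no steroid dose and leaves the response categories as they are.

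The cost is amendment wording, a dose field on the imaging form and one extra analysis. The downside is that for children on steroids the MRI is booked later within the existing 14-day window.
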